Is more than one institution located in the United States (another university, commercial institution, etc.) engaged in this research proposal? (required)

Study Overview

Anticipated end date for collecting data: 2019-01-31

Anticipated end date for analyzing data: 2021-12-31

Is this research funded? Yes

Funding Source(s): Federal government

Supply all Agency Grant Numbers & Titles currently associated with this protocol:

NIMH R34MH106770

Do any of the Funding Sources create a Conflict Of Interest for the Principal Investigator, Faculty Sponsor or Research Team (Sub-Investigators) listed on this protocol? No

What is the purpose in conducting this research? How does this study contribute to the advancement of knowledge and why is it worth doing?

Approximately half of the U.S. population experiences serious mental health problems during their lifetime, including 29% with anxiety pathology severe enough to qualify for an anxiety disorder diagnosis. Critically, more than two thirds of individuals struggling with a mental illness do not receive treatment. With this level of mental illness burden, it is clear that treating people one-on-one in an office setting will never meet the existing needs. There are many barriers to treatment, including costs, difficulties accessing evidence-based treatments in many regions, and associated stigma. Thus, there is a pressing need to consider alternative, larger scale approaches to delivering mental health services. Cognitive Bias Modification (CBM) interventions hold considerable promise as a way to meet these needs, especially for anxiety difficulties. These computer-based programs are designed to alter biased ways of thinking, such as a tendency toward negative interpretations, which cause and maintain anxiety. Because these programs do not require therapist contact and can be administered on any computer with an Internet connection, CBM holds promise as a cost-effective method that can be disseminated widely. However, while CBM for interpretation bias (CBM-I) has established efficacy when administered in-person in the laboratory, it now needs to be tested with broader populations using a web-based infrastructure to examine: a) whether the program will be effective in a web environment, b) whether the program continues to engage the targeted mechanism (i.e., interpretation bias), c) the feasibility of this delivery method, and d) the modifications needed to adapt the program for the web (in particular, to prime anxiety-linked negative thinking in an online environment, we test the effect of adding a guided anxious imagery exercise to prime feared outcomes prior to each training session).

What will participants do in this study? Please provide an overall summary of the study plan. Where and when it will be conducted? What do you hope to learn from these activities? If the study has more than one phase, clearly map out the different phases. You will be required to describe the study components in more detail in later sections but use this paragraph to help your IRB reviewer to understand the general outline of the study. Other sections in the protocol form can be seen below.

Approximately half of the U.S. population experiences serious mental health problems during their lifetime, including 29% with anxiety pathology severe enough to qualify for an anxiety disorder diagnosis. Critically, more than two thirds of individuals struggling with a mental illness do not receive treatment. With this level of mental illness burden, it is clear that treating people one-on-one in an office setting will never meet the existing needs. There are many barriers to treatment, including costs, difficulties accessing evidence-based treatments in many regions, and associated stigma. Thus, there is a pressing need to consider alternative, larger scale approaches to delivering mental health services. Cognitive Bias Modification (CBM) interventions hold considerable promise as a way to meet these needs, especially for anxiety difficulties. These computer-based programs are designed to alter biased ways of thinking, such as a tendency toward negative interpretations, which cause and maintain anxiety. Because these programs do not

require therapist contact and can be administered on any computer with an Internet connection, CBM holds promise as a cost-effective method that can be disseminated widely. However, while CBM for interpretation bias (CBM-I) has established efficacy when administered in-person in the laboratory, it now needs to be tested with broader populations using a web-based infrastructure to examine: a) whether the program will be effective in a web environment, b) whether the program continues to engage the targeted mechanism (i.e., interpretation bias), c) the feasibility of this delivery method, and d) the modifications needed to adapt the program for the web (in particular, to prime anxiety-linked negative thinking in an online environment, we test the effect of adding a guided anxious imagery exercise to prime feared outcomes prior to each training session).

- Together, the current proposal will develop an infrastructure to pilot test the effectiveness of web-based CBM-I for anxiety symptoms. CBM-I training will target moderate to severe anxiety symptoms, a widespread problem area with considerable occupational and social impairment. Participants will be visitors to Project Implicit Mental Health (PIMH; soon to be renamed Project Implicit Health), an existing website directed by the Principal Investigator that allows visitors to assess their cognitive biases tied to mental health concerns. Consistent with the RFA's priorities, this approach encourages efficiencies by capitalizing on the existing PIMH site and its heavy traffic. Further, the site's large number of visitors and use of automated assessments will make it efficient to assess baseline demographic characteristics and interpretation bias as moderators of CBM-I effects that can be tested in future trials.
- **Aim 1:** Develop and evaluate usability and acceptability of web-based CBM-I for anxiety symptoms. Aim 1 will build the web-based interpretation bias training program using the PIMH infrastructure. We will pilot the program on a small test group of moderate to highly anxious participants (N=15) who will complete questionnaires and semi-structured interviews to provide feedback on the programs' usability and acceptability. Further, an advisory board (N=8) of anxiety researchers, clinicians, and experts in CBM and web-based research will provide feedback on the program and study protocol. Using a "deployment-focused" approach, this feedback from experts and end-users will be used to iteratively modify the program for the trial planned for Aims 2 and 3. Thus, even at this initial pilot stage, we will measure the targeted outcome (anxiety symptoms) and mechanism (interpretation bias) to determine whether modifications to enhance target engagement are needed. Note, within RDoC, this outcome falls under the Potential Threat/Anxiety construct within the Negative Valence System, and the targeted mechanism (interpretation bias) falls under the Response Selection, Inhibition construct within the Cognitive (effortful) control system. Both the outcome and mechanism will be objectively measured using multiple units of analysis (e.g., behavior and self-report). Further, mechanisms underlying the guided anxious imagery prime's effects will be measured by assessing subjective distress, imagery vividness, and activation of feared outcomes following the manipulation. This prime was selected in part because of its potential to be disseminated widely in future trials, given it does not require human contact.
- **Aim 2:** Test target engagement, feasibility and effectiveness of web-based CBM-I.
- **Aim 3:** Evaluate the impact of an anxious prime on web-based CBM-I for anxiety symptoms.
- Aims 2 and 3 will test the feasibility of an 8-session web-based interpretation training program called "MindTrails" among individuals with moderate to severe anxiety symptoms (based on screening at the PIMH site). Participants will be randomly assigned to either active CBM-I (100% positive scenario training) or a 50% positive/50% negative condition, or a no scenario control condition. Half the participants in each of these 3 conditions will receive an anxious imagery prime prior to each training session, and half will receive a neutral imagery prime, resulting in a 3 training condition x 2 prime design. Feasibility will be determined by analyses of recruitment, attrition, acceptance of randomization, adherence to and appropriateness of the measurement model, caseness, extent of missing data, and safety. Additionally, target engagement (change in interpretation bias) and preliminary tests of effectiveness at reducing anxiety symptoms will be evaluated.
- Furthermore, a group of up to 10 participants will be randomly selected to receive the additional benefit of coaching. These participants will be contacted through email and directed to a separate consent form regarding the coaching protocol. The coaching protocol itself will involve a series of brief phone calls and/or Google Voice messaging sessions with the purpose of increasing adherence to the MindTrails program. The coaching contacts will involve discussing goals for login and site use, reinforcing use, and addressing questions about the site's functionality and applicability. This is not therapy by phone and participant disclosure of symptoms will not be required. We will use undergraduate and graduate student-level coaches and will follow an adapted version of the standard training protocol for TeleCoach (with consultation from [name], developer of the intervention). The coaching protocol has already been approved in UVA IRB SBS protocol 2017-0234-00. Including this additional service is expected to help refine the coaching protocol as well as increase adherence to the program.

- **Materials:**

- *Cognitive Bias Modification for Interpretations (CBM-I).* A modification of the paradigm used by Mathews and Mackintosh (2000) involving the ascription of threat meanings to ambiguous scenarios will be used to train interpretation biases. Note that similar procedures have been used in already approved protocols (e.g., Protocol # 2007028100 "Finishing Stories," Protocol # 2009028500 "Heights Fear Reduction," and Protocol # 2011039200 "Finishing Brief Stories").
- Participants will be asked to read about and then imagine themselves in approximately a series of different situations involving ambiguous anxiety-relevant scenarios. At the end of each scenario, participants will be asked to complete a word fragment (which has only one solution) that resolves the meaning of the preceding text in a positive or negative direction, depending on the condition. For example, participants reading a positive interpretation scenario would read, "Your partner asks you to go to an anniversary dinner

that their company is holding. You have not met any of his/her work colleagues before. Getting ready to go, you think that the new people you will meet will find you friendly." Participants would then complete the fragment with the word "friendly." For the equivalent negative interpretation scenario, participants would read the same scenario, but the word fragment would be "b_oring," which participants would complete with the word "boring." All participants would then read the same comprehension question, to insure that they had made the correct interpretation. For the above example, participants would be asked "Were you disliked by your new acquaintances?"

- To maintain participants' interest across sessions (and attain desirable difficulty to enhance learning; see Hertel & Mathews, 2011) we may change the number of missing letters in word fragments (e.g., word fragments may be missing only 1 letter in the first 4 sessions, and 2 letters in the second 4 sessions).
- Depending on condition, participants may either complete all positive versions of the scenarios ("active CBM-I"), half positive/half negative versions of the scenarios ("50/50"), or not complete any training scenarios ("imagery only, no scenarios").
- *Recognition Ratings* (modified from Mathews & Mackintosh, 2000). To measure interpretation bias, participants will read ~9 ambiguous scenarios with titles. After, participants will see the titles of each scenario, followed by 2 disambiguated interpretations of the scenario: 1 positive and 1 negative. Participants will be asked to rate each disambiguated interpretation based on how similar in meaning it is to the original scenario. Depending on available time, participants may also see 2 additional disambiguated interpretations of each scenario that are unrelated to anxiety (labeled "foils") to evaluate specificity of training effects.
- *Brief Body Sensations Interpretation Questionnaire* (BBSIQ; Clark et al., 1997). The BBSIQ is a 14-item version of the Body Sensations Interpretation Questionnaire, which is modified from McNally and Foa's (1987) Interpretation Questionnaire. In the present study, very minor wording modifications were made to make the measure more prototypic of American rather than British English. Participants are presented with ambiguous events and then asked to rank order three alternative explanations for why the event might have occurred. One option is always negative, whereas the other responses are either neutral and/or positive. Half of the items refer to events consistent with the theoretical prediction of a catastrophic misinterpretation of bodily sensations (referred to as 'Panic' items), and the remaining items (referred to as 'External Threat' items) reflect other potentially threatening events (related mainly to fears of negative social evaluation). An example of a panic item is, "You notice that your heart is beating quickly and pounding." The three alternative explanations are, "because you have been physically active," "because there is something wrong with your heart," or "because you are feeling excited." Participants rate the extent to which they believe each of the explanations on a 0-8 Likert scale.
- *Imagery Primes*. Participants will be randomly assigned to complete either an anxious imagery prime (where they do a guided imagery exercise imagining an upcoming anxiety-provoking situation to prime feared outcomes) or a neutral control imagery exercise (where they do a guided imagery exercise imagining upcoming mundane tasks, like brushing one's teeth or getting dressed, that is matched for time and simulation of a future event). See Appendix for scripts. The choice to test an anxiety prime as a key modification of lab-based CBM for the web follows results from a recent CBM study of attention training for social anxiety administered on the web, which found that the group instructed to activate social anxiety fears prior to each CBM training session achieved greater anxiety symptom reduction than both a control CBM group and a group doing CBM without the anxiety prime, and even did as well as a full web-based CBT condition. Further, the gains remained at a 4-month follow-up assessment. These results strongly support the argument that one reason some prior CBM (for attention) studies have not shown strong results on the web is due to lack of emotion or bias activation on the web. The choice to use imagery for the prime is based on the ease with which this can be administered online in an automated way so that it can ultimately be scaled up for broad dissemination. Also, imagery can readily activate feared outcomes (e.g., catastrophic thinking), which is expected to strengthen training as people practice new ways of thinking while the biases are activated.
- *Measuring Impact of Imagery Primes*. Following the anxious or neutral imagery prime, participants will be asked to estimate the probability that the situation they imagined will turn out well or badly, and their ability to manage that situation. We will also assess subjective distress (using the Subjective Units of Distress Scale) and vividness of the image.
- **Procedure for Aim 1:** Once the materials and training programs (termed the "MindTrails" Project) are fully assembled and ready for testing, we will solicit feedback from two groups: 1) a small test group of highly anxious participants (who will be compensated \$40 for their study visit, which will last approximately 2 hours); 2) an expert advisory board (who we do not plan to provide with financial compensation, given they will be participating as a professional courtesy). Both groups will try out the tasks and complete the measures to provide feedback on the programs' usability and acceptability via a survey and semi-structured interview (see above measures). We will assess numerous aspects of user experience, including clarity of the materials, ease of navigating the site, appropriateness of the intervention materials (re. language used, targets selected for stimuli), affective response to the materials, and extent materials are engaging and acceptable, perceived measurement burden of the assessment battery, etc. The semi-structured interview for each participant will follow completion of the user experience questionnaire, so that the interviewer can probe the responses and ask follow-up questions about potential ways to address the identified weaknesses of the program (e.g., participants' ideas about ways to make the tasks more engaging, the instructions clearer, etc.). These interviews will be conducted by the PI or trained project staff and graduate student collaborators on the project. This feedback will be used to modify all aspects of the programs in preparation for Aims 2 and 3.
- Note, we will also pilot the MindTrails site materials (e.g., CBM scenarios) on mobile phones using analogous procedures.

- **Procedure for Aims 2 and 3:** This study will be completed over the Internet, through an extension of Project Implicit Mental Health (www.implicitmentalhealth.com). Participants will be individuals recruited directly from the Project Implicit Mental Health website, as well as those who are invited to the site through a variety of online and offline advertisements and outreach efforts. The target population will be adults age 18 and over who score in the moderate to extremely severe anxiety range (i.e., 10 or higher) on the Depression, Anxiety, Stress Scales – Short Form: Anxiety Subscale (DASS21-AS).
 - If individuals score above the established cutoff during their Project Implicit Mental Health study, they will be alerted to their eligibility for this study via a message added to their standard debriefing form following completion of the anxiety and depression study measures. (See attached Debriefing forms to see additions to the standard Project Implicit Mental Health form). Individuals may also see if they're eligible for the study by clicking an icon at the front page of the Project Implicit Mental Health site.
 - Following consent, participants who are eligible will be randomly assigned to one of 6 groups (active CBM-I + anxiety imagery prime, 50/50 + anxiety imagery prime, no scenario control + anxiety imagery prime, active CBM-I + neutral imagery prime, 50/50 + neutral imagery prime, no scenario control + neutral imagery prime condition), matched for gender ratio. Participants will be asked to complete eight sessions of their assigned intervention, over the course of four weeks (~two sessions per week). Each session will last approximately 20 minutes.
 - Prior to the first session, participants will receive a rationale about the intervention, followed by a series of questionnaires and online tasks assessing psychological symptoms, mental health history and demographics, interpretation bias, quality of life, etc. Following the third, sixth, and eighth sessions, participants will also be asked to complete the assessment battery. Finally, two months after the intervention, participants will be asked to complete a follow-up assessment, before being debriefed and provided with feedback about their change in symptom scores. Please see Measures Schedule in the Appendix for list of specific measures at each time point.
 - Following completion of the first training session, up to 10 participants will be randomly selected to receive coaching. These participants will be emailed upon their selection and directed to a separate consent form. After completion of the consent process, participants will participate in weekly sessions with their coaches. These sessions will be used to discuss usability and engagement issues with the MindTrails program and will be held either over the phone or through Google Voice messaging. Coaching will stop after the (eighth) MindTrails session. We will offer \$40 to participants for taking part in coaching.
 - If participants are randomly assigned to a control condition, they will be offered the opportunity to complete one of the actual interventions following completion of the study.

Is this study topic relevant to cancer risk factors, prevention, cancer treatment, or survivorship (e.g., pain, financial toxicity etc.), or will the study purposefully include participants currently or previously diagnosed with cancer, or their caregivers (required)

(optional) **Study Overview file upload:** Below you have the option to upload additional files to help the Board better understand your study. You are not required to provide any additional explanation beyond completing the text boxes provided in this Study Overview section; however, for example, if you are using a new technology or a complicated process that would be more easily demonstrated with image or video, you can upload the file here.

Participant Groups

Participant Group Name: Anxious participants

Age Range (years): 18 and older

Vulnerable populations: includes students

Maximum number of participants, in this group, expected to enroll over the life of the study: 1800

Minimum number of participants, in this group, expected to enroll over the life of the study: (required)

Total number of participants, in this group, ever enrolled: 1710

Approximate number of participants, in this group, currently enrolled: 0

Future Enrollment: We are performing data analysis only, in this group (i.e. we are not actively collecting data from participants in this group)

Have participants, in this group, withdrawn from the study in the past year? No

Describe the participants in this group.

Gender: Mixed
Race: All/any
Estimated number of participants: 1000 (plus ~100 MTurk pilot participants)

The target populations for Aims 2 and 3 will be adults aged 18 and older who experience distress and/or impairment following from symptoms of anxiety. They will be selected based on established cut points on symptom screening measures. Specifically, the DASS21-AS will be used to determine eligibility. Individuals who score 10 or higher (suggesting moderate to extremely severe anxiety) on this measure at will be invited to participate in the study. Participants will be recruited via online recruitment methods (Craigslist, Project Implicit Mental Health, Facebook, etc.)

Depending on participant interest and management of technical issues, we may allow participants who are not eligible (based on the DASS21-AS score) to still complete the intervention (without the assessments and without payment) if they would like. (These would not be study participants.)

Additionally, approximately 100 participants will be recruited via Amazon's mTurk to pilot study materials (e.g., rate how positive or negative stimuli are). These participants will not be screened for anxiety, although they will see the same consent and debriefing information as other participants. These participants will be paid \$2.00 for their time. See protocol #2013020200 for more information about Amazon's mTurk. We will approve payment to all participants who complete the study, following mTurk protocol. We will also pay participants who contact us via email saying that they withdrew from the piloting study and would like to receive payment.

Will participants in this group be compensated for taking part in your study? Yes

Are any of the participants US citizens or US residents? Yes

This question applies only to participants who are US citizens or US residents.

Will participant payments be processed through an account administered by UVA? No

Describe your payment process, including information about the amount participants will be paid and how payment will be issued and delivered to participants.

The Amazon mTurk participants will be paid \$2.00 for their time. We will approve payment to all participants who complete the study, following mTurk protocol. We will also pay participants who contact us via email saying that they withdrew from the piloting study and would like to receive payment.

Participant Group Name: Pilot participants

Age Range (years): 18 and older

Vulnerable populations: no vulnerable population (none)

Maximum number of participants, in this group, expected to enroll over the life of the study: 23

Minimum number of participants, in this group, expected to enroll over the life of the study: (required)

Total number of participants, in this group, ever enrolled: 22

Approximate number of participants, in this group, currently enrolled: 0

Future Enrollment: We are performing data analysis only, in this group (i.e. we are not actively collecting data from participants in this group)

Have participants, in this group, withdrawn from the study in the past year? No

Describe the participants in this group.

In Aim 1, which focuses on development of the web-based interpretation bias and attention bias training programs, we will pilot the program tasks and materials on a small test group of moderate to highly anxious participants (N=15). Aim 1 pilot anxious participant will be recruited via online recruitment methods (e.g., Craigslist) to obtain a sample that will be as comparable as possible to the sample planned for Aims 2 and 3.

These individuals will be selected based on established cut points on the symptom screening measure, the Depression, Anxiety, Stress Scales – Short Form: Anxiety Subscale (DASS21-AS; Lovibond & Lovibond, 1995). Individuals who score 10 or higher (suggesting moderate to extremely severe anxiety) will be invited to participate. Further, an advisory board (N=8) of anxiety researchers,

clinicians, experts in Internet interventions, and experts in CBM will provide feedback on the programs. These individuals will be recruited through personal invitations by the PI and study team.

Will participants in this group be compensated for taking part in your study? Yes

Are any of the participants US citizens or US residents? Yes

This question applies only to participants who are US citizens or US residents.

Will participant payments be processed through an account administered by UVA? Yes

Participants are paid using UVA funds issued as: A

A: Oracle issued check for any amount and can have ID linked to check.

Describe your payment process, including information about the amount participants will be paid and how payment will be issued and delivered to participants.

The anxious pilot participants will be compensated \$40 for their study visit and compensation will be issued by check. We do not plan to provide the expert advisory board participants financial compensation, given they will be participating as a professional courtesy.

Participant Summary

Participant Group Name: Anxious participants

Maximum number of participants, in this group, expected to enroll over the life of the study: 1800

Participant Group Name: Pilot participants

Maximum number of participants, in this group, expected to enroll over the life of the study: 23

What special experience or knowledge does the Principal Investigator, Faculty Sponsor, and the Research Team (Sub-Investigators) have that will allow them to work productively and respectfully with the participants in this protocol and/or participant data?

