There are no direct benefits for participating in the study. However, the primary goal of the proposed research is to determine the feasibility of the proposed intervention and to gain knowledge about ways to maximize its effects (e.g., by exploring whether baseline bias or symptom severity moderates effects, etc.). Secondarily, participants in the active CBM conditions may also experience a reduction in cognitive biases and anxiety symptoms that persists after training, based on the promising lab-based findings for CBM in anxious samples. Thus, we believe that any risks of discomfort associated with the interventions would be offset by what will be learned regarding the potential for future widespread dissemination of a cost-effective intervention. Additionally, participants in all conditions will receive links to referral information in the Debriefing forms, which could help those in need of further care to access treatment. During debriefing, participants will also be given psychoeducation regarding the interplay between biased cognitive processing and symptomatology. Therefore, in light of the potential benefits, the risk of participation appears justified.

Continuation

Are you applying for a continuation of your protocol's approval? Yes

Was this project undertaken? Yes

Are there any additional risks to participants or new information about risk to participants in the study not described in the previously approved protocol? No

Describe what you did during the past year:

Data collection for this study ended in January 2019. Data analysis is ongoing.

In addition, go to the Participant Groups section and provide updated information regarding participant enrollment.

Modification

Does this protocol version include any changes that were made to the previously approved protocol (protocol form, consent documents, etc)? Minor edits are considered changes! No

Unexpected Adverse Events

Did a negative event associated with the research occur and does it meet one of the following conditions:

is not described as a possibility in the previously approved protocol OR;

did not occur within the parameter described (i.e. an increase in frequency or severity)?

No

Questions: IRB-SBS Help Desk

University of Virginia
Office of the Vice President for Research
Human Research Protection Program
Institutional Review Board for Social & Behavioral Sciences

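### Can the outcome-probability and coping ratings show that the anxious prime activated feared outcomes, when each prime arm rates a different imagined situation?

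*Combined protocol and SAP*

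**What the plan says.** The relevant text is in the Combined protocol and SAP, Study Overview.

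- **The two primes (Materials, Imagery Primes).** One arm does a guided exercise "imagining an upcoming anxiety-provoking situation to prime feared outcomes". The other does an exercise "imagining upcoming mundane tasks, like brushing one's teeth or getting dressed", matched on duration and on simulating a future event.
- **The ratings (Measuring Impact of Imagery Primes).** After either prime, participants "estimate the probability that the situation they imagined will turn out well or badly" and rate their ability to manage that same situation. The paragraph adds: "We will also assess subjective distress (using the Subjective Units of Distress Scale) and vividness of the image".
- **Purpose.** The Aim 1 bullet says the prime's mechanisms will be measured by "assessing subjective distress, imagery vividness, and activation of feared outcomes following the manipulation". The Imagery Primes paragraph explains why the prime should help: "imagery can readily activate feared outcomes (e.g., catastrophic thinking), which is expected to strengthen training".
- **Status (Continuation).** "Data collection for this study ended in January 2019. Data analysis is ongoing".

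The prime scripts, the Measures Schedule and the approved measures file are cited but are not part of the available text. That text gives no statistical model or test for any of the post-prime ratings.

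**The concern.** The Aim 1 bullet names three things to be measured after the prime: distress, vividness and activation of feared outcomes. The Measuring Impact paragraph lists distress and vividness as separate items. By elimination, the outcome-probability and ability-to-manage ratings look like the measure of the third.

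Those two ratings have no common object. A feared event may be rated as likelier to go badly and harder to manage than brushing one's teeth even if the prime has activated nothing. Randomisation balances the people in the two arms. It does not balance what they rate, because that is part of the assigned condition.

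If the gap were reported as proof of activation, the trial would claim a mechanism that these items cannot isolate. That matters for Aim 3, because activation is the stated reason for expecting the prime to strengthen training. With no analysis rule in the available text, nothing explicitly rules out that reading.

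**Working it through.** The documents give no power, alpha or effect size for the prime check, so there is no figure to reproduce. The question is first one of reading; the arithmetic only shows how easily a content-only gap could reach significance.

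**1. Is the rated object arm-specific?** Yes. Both ratings refer to the participant's own imagined situation, which is anxiety-provoking in one arm and mundane in the other. The vividness rating also concerns an arm-specific image. No rating before the prime and no situation common to both arms is described, but the scripts and measures file are not available, so their absence is not established.

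**2. How often would a content-only gap be significant?** Inputs:
- 500 per prime arm: the estimated 1000 participants (Participant Groups, Anxious participants), halved because half of each training condition gets each prime.
- 855 per prime arm: the 1710 ever enrolled in the same group, halved. This is an upper limit, since it ignores attrition.
- 100 per prime arm: assumed, for heavy loss of ratings.
- Two-sided alpha 0.05, SD 1, one comparison, and shifts *d* of 0.1 to 0.3 SD: all assumed.

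Formula (normal approximation): power ≈ Φ(*d*·√(*n*/2) − 1.96).

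- *n* = 500, *d* = 0.1: 0.1 × 15.81 − 1.96 = −0.38, giving 0.352.
- *n* = 500, *d* = 0.2: 3.16 − 1.96 = 1.20, giving 0.885.
- *n* = 500, *d* = 0.3: 4.74 − 1.96 = 2.78, giving 0.997.

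| Per arm | *d* = 0.1 | *d* = 0.2 | *d* = 0.3 | Shift significant in 80% of trials |
|---|---|---|---|---|
| 100 (t-test) | 0.108 | 0.291 | 0.560 | 0.398 SD |
| 500 | 0.352 | 0.885 | 0.997 | 0.177 SD |
| 855 | 0.543 | 0.985 | >0.999 | 0.135 SD |

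The last column for 500 and 855 is (1.96 + 0.842)·√(2/*n*): 2.802 × 0.0632 = 0.177 and 2.802 × 0.0484 = 0.135.

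These are generic two-sample figures. They show that a modest content difference would be detected in a trial this large. They do not show how big the content difference is here; the documents do not say.

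**3. Does the plan draw the invalid conclusion?** Not in the available text.
- No section states a between-arm test of the two ratings.
- No section names them as the measure of activation of feared outcomes; that link is inferred by elimination.
- The sentence on mechanisms sits in the Aim 1 bullet, which describes a 15-person usability pilot. Use in Aim 3 is plausible, since the Materials section covers the whole project, but it is not stated.

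**4. Does any trial result depend on these ratings?** The comparison of prime arms on anxiety symptoms and interpretation bias uses other measures and rests on randomisation alone. Risks & Benefits gives feasibility as the primary goal. No mediation analysis through these ratings is described.

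**The case for a change.** The strongest case for a change is that the measurement point is correct and a safeguard would cost nothing. Analysis was still under way, no new data would be needed, and a sentence could make distress on the SUDS the between-arm check, keep the two situation ratings for use within the anxious-prime arm, and bar reading their between-arm gap as activation. Under a heading about measuring the primes' impact, the natural analysis is anxious versus neutral, so the misreading is easy to make.

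The measurement point stands: the gap alone does not show activation. The proposed rule is not clearly better than leaving the matter to the analyst, for three reasons.

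- **SUDS is not a sure substitute.** Its wording is not in the available text. If it asks about current distress, the arms can be compared. If it asks about distress within the imagined scene, the same objection applies. Even at best it measures distress, a different construct from feared outcomes.
- **The within-arm check is weak.** Deciding that the anxious situation was seen as threatening needs a reference or a threshold. The neutral arm is the only reference described, and the proposal removes it without supplying a threshold.
- **The between-arm comparison has a proper use.** The imagined content is the manipulation. Showing that one arm imagined something it expected to go worse and to be harder to handle is an ordinary check that the assigned imagery was delivered. A bar on reading the gap as activation should not cost the trial that check.

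**Conclusion.** No change is needed. The two ratings refer to arm-specific situations, so a between-arm difference can support a statement that the imagery content differed as intended, but not by itself a statement that feared outcomes were activated. The available text does not make the second statement or plan an analysis that would. This is a gap that an analyst fills sensibly when writing up a manipulation check. If the unseen measures contain a rating of the same situation in both arms, that item is the natural one for feared-outcome activation.

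The effect on the randomised comparisons of anxiety and interpretation bias is nil. The possible effect on a manipulation-check report is a significant content-only gap in about 35% to 99.7% of trials at 500 per arm, or 11% to 56% at 100 per arm, for assumed shifts of 0.1 to 0.3 SD. Those figures rest on the assumed shifts, on a single two-sided 5% comparison and, for the smaller size, on an assumed number of raters. The conclusion does not rest on them. It rests on the absence of any stated between-arm inference from these items, and would need another look if the unseen measures or a separate analysis document set one out.
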